20.4.8 Additional Endpoints

Additional Procedural Data will be analyzed overall and per procedure type (atrial ablation/ventricular ablation) using the PP Analysis Set and include the following parameters:

- Whether Imaging for Left Atrium (LA) and Left Ventricle (LV) volume measurements was done;
- Total fluoroscopy time;
- Total duration of the procedure.

For each of the above procedural data, the denominator will be the number of subjects where assessments with the study device are performed.

Listings will be provided.

Additional safety data

All non-serious AEs not related to the investigational catheter will be listed by System Organ Class and Preferred Term, severity, causality (defined as possible, probable or having a causal relationship to the device and/or procedure), anticipation and outcome.

20.4.9 Handling of Missing Data

No missing data will be imputed in this study. All analyses will be performed using observed data.

21. Ethics and Protection of Human Subjects

21.1 Ethical Standard

As the Sponsor of this study, Biosense Webster has the overall responsibility for the conduct of the study, including assurance that the study meets the regulatory requirements of the Food and Drug Administration (FDA), applicable European medical device regulation and the local government. For study under MDR, MDR2017/745 will be applicable, amending Directive 2001/83/EC, Regulation (EC) No 178/2002 and Regulation (EC) No 1223/2009 and repealing Council Directives 90/385/EEC and 93/42/EEC.

The Sponsor will also maintain compliance with GCP (ICH E6 (R2), 9 November 2016), the European standard EN ISO 14155 (Clinical Investigation of Medical Devices for Human Subjects), the Declaration of Helsinki (Ethical Principles for Medical Research Involving Human Subjects, Fortaleza 2013), Sponsor general duties (21 CFR 812.40), selection of investigators (21 CFR 812.43), monitoring (21 CFR 812.46), supplemental applications (21 CFR 812.35 [a] and [b]), maintaining records (21 CFR 812.140 [b]), and submitting reports (21 CFR 812.150 [b]), and to local regulations where required.

- **General Duties**
Biosense Webster's general duties consist of submitting the clinical investigation application to appropriate regulatory agencies, assuring that sites have received EC approvals prior to shipping the devices, selecting investigators, ensuring proper clinical site monitoring and ensuring subject informed consent is obtained.
- **Data Quality and Reporting**
Biosense Webster is responsible for providing quality data that satisfy federal regulations and informing proper authorities of serious unanticipated AEs and deviations from the protocol.
- **Selection of Investigators**
All potential investigational sites will undergo an evaluation to ensure that the site has the appropriate facilities and personnel to conduct the study in compliance with the clinical investigational plan. Based on outcome of evaluation process, Biosense Webster will select qualified investigators, ship devices only to participating investigators, obtain a signed Investigator's Agreement and provide the investigators with the information necessary to conduct the study.
- **Supplemental Applications**
As appropriate, Biosense Webster will submit changes in the Clinical Investigational Plan to the investigators to obtain all applicable re-approvals.

- **Maintaining Records**
Biosense Webster will maintain copies of correspondence, data, adverse device effects and other records related to the study. Biosense Webster will maintain records related to the signed Investigator Agreements.
- **Submitting Reports**
Biosense Webster will submit any required regulatory reports identified in this section of the regulation. This may include UADEs, withdrawal of EC approval, current investigators list, annual progress reports, recall information, final reports and protocol deviations.

21.2 Informed Consent Process

21.2.1 Informed Consent Procedure and Documentation

Subjects informed consent must be obtained and documented according to the principles of informed consent in the latest version of the Declaration of Helsinki (Fortaleza, 2013), ISO 14155, and approved by the reviewing CA and EC.

Informed consent is mandatory and must be obtained from all subjects prior to their participation in the study.

Prior to screening or performing any study related procedures that are solely for the purpose of determining eligibility for this study, any potential benefits and risks of the study must be explained to the subject. Subjects will be informed about aspects of the study that are relevant to the subject's decision to participate. Subjects should be made aware that by signing the ICF, they are granting approval for study personnel to review their medical records and to collect/analyze personal medical information. Subjects should also be informed that study personnel will maintain confidentiality of the medical records at all times.

The ICF will be written in a native, non-technical, language that is understandable to the subject and is to be approved by the applicable EC prior to enrolling subjects. The subject or designee will be provided with ample time to read and understand the ICF and to consider participation in the study. Informed consent will be requested prior to enrollment and must be personally signed and dated by the subject, or subject's legal representative, prior to performance of any study related activity or procedure. If a subject is unable to read or write, informed consent shall be obtained through the aid of an independent witness who will be present throughout the process. The written ICF and any other information shall be read aloud and explained to the prospective subject and, whenever possible, subject shall sign and date the ICF. The witness must also sign and date the ICF attesting that the information was accurately explained, and that informed consent was freely given. The point of enrollment corresponds with the time that the subject signs the informed consent.

The investigator and/or designee must also clearly document the process of obtaining informed consent in the subject's source documents. The voluntary process of obtaining informed consent confirms the subject's willingness to participate in the study. It's the investigator's responsibility to ensure that the informed consent process is performed in accordance with ICH-GCP and, where applicable, local and federal regulations. Subjects should not be coerced, persuaded, or unduly influenced to participate or continue to participate in the trial. Subjects or his/her legal representative must be given ample time and opportunity to inquire about details of the trial and all questions about the trial should be answered to the

satisfaction of the patient or the representative. Failure to provide written informed consent renders the subject ineligible for the study. If new information becomes available that can significantly affect a subject's future health and/or medical care, this information shall be provided to the subject(s) affected in written form. If relevant, all affected subjects shall be asked to confirm their continuing informed consent in writing by dating and signing the amended ICF.

21.3 Participant and Data Confidentiality

During this clinical investigation, all representatives of the Sponsor will comply with all in-country privacy laws and regulations regarding contact with subjects, their medical record information, copying of information, and protection of the subject identities.

All information and data sent to Biosense Webster concerning subjects or their participation in this clinical investigation will be considered confidential. Only authorized Biosense Webster personnel or representatives (including contracted service providers, i.e. Core Lab, Clinical Research Associate, CRO, etc.), representatives of the FDA or CAs acting in their official capacities will have access to these confidential files upon request (including, but not limited to, laboratory test result reports, ECG reports, admissions/discharge summaries for hospital admission occurring during a patient's study participation and autopsy reports for deaths occurring during the clinical investigation). Some of the countries to which the study subjects and investigators personal data may be transferred may not offer as comprehensive a level of protection of personal data as within the European Union but Sponsor will take all reasonable steps to ensure a sufficient level of data protection. All data used in the analysis and reporting of this evaluation will exclude identifiable reference to the subject.

21.3.1 Research Use of Stored Data

- Intended Use: Data collected under this protocol may be used to study AF.
- Storage: Access to stored data will be limited. Data will be stored using codes assigned by the sponsor. Data will be kept in password-protected computers. Only investigators and the sponsor will have access to the data.

22. Source Documents and Access to Source Data/Documents

Data entered on to the eCRFs will be taken from source documentation, such as hospital procedure reports, admission and discharge summaries, other hospital or investigator office/clinic documents, and system data (CARTO and ultrasound system). If unique study parameters are not documented on standard hospital or office reports, a worksheet may be developed to record this information. The worksheet shall be signed by the PI or authorized designee and will serve as source document and as basis for monitoring the eCRFs. Electronic subject records will be considered as source documents on the condition that the hospital's database is a validated system. If this is not the case, electronic records should be printed and added to the subject's paper file. A print-out of a completed eCRF cannot be used as source documentation.

Investigators should maintain information in the subject's medical records, which corroborate data collected on the eCRFs. In order to comply with these regulatory requirements, at minimum, the following is a list of information that should be maintained.

- Medical history/physical condition of the study subject before involvement in the study sufficient to verify protocol selection criteria (if not already present).

- Dated and signed notes from the day of entry into the study including the study Sponsor (Biosense Webster), protocol number, clinical site, subject number assigned and a statement that consent to participate in the study was obtained.
- Dated and signed notes from each study visit with reference to the eCRFs for further information, if appropriate (for specific results of procedures and exams).
- Reports on AEs and their resolution, including supporting documents such as discharge summaries, EP lab reports, ECGs, lab results.
- Notes regarding protocol-required medication and prescription medications taken during the study (including start and stop dates).
- Notes on subject's condition upon completion of or withdrawal from the study.

Only authorized Biosense Webster personnel or representatives, authorized site personnel, local government authorities, or the FDA, acting in their official capacities, will have access to these confidential files.

23. Quality Assurance and Quality Control

Quality Control (QC) procedures will be implemented beginning with the data entry system and ongoing QC checks will be run on the database. Any missing data or data anomalies will be communicated to the site(s) for clarification/resolution.

Following written SOPs, monitors will verify that the clinical trial is conducted and data are generated, documented, and reported in compliance with the protocol, GCP, and the applicable regulatory requirements. If noncompliance is identified, Sponsor is required by regulation to implement measures to secure compliance.

The investigational site will provide direct access to all trial related sites, source data/documents, and reports for the purpose of monitoring and auditing by the sponsor, and inspection by local and CAs.

24. Data Handling and Record Keeping

24.1 Data Collection and Management Responsibility

The Sponsor will be responsible for all data management activities. These activities include development of an EDC system and utilizing a validated EDC system into which all study data will be entered. The Sponsor will be responsible for reviewing all data to ensure the overall integrity of the database.

24.1.1 Data Collection

eCRFs will be used to collect all subject data during this clinical investigation. eCRFs have been developed to capture the information outlined in this clinical investigation Plan. Modification to the eCRF will only be made if deemed necessary by the sponsor. Data on these eCRFs will be monitored (source verified) and the monitor will ask the site representative to correct if necessary, to match the source documents. All changes made to the data will be tracked in the electronic audit trail. The investigator will be required to sign designated eCRFs as verification that they have been reviewed and the data entered are correct. Data from these eCRFs will be used to provide analysis of this clinical investigation.

24.1.2 Data Reporting

The investigator, or a designated individual, is responsible for ensuring that clinical investigation data are timely and properly recorded on each subject’s eCRF and related documents. The investigator, or a designated individual, is required to electronically sign the eCRF on the appropriate pages to verify that he/she has reviewed and attests to the correctness of the recorded data. Completed eCRF will be reviewed and monitored by the sponsor personnel, or an appropriately qualified and trained designee, throughout the clinical investigation. To this end, the Investigator and institution must permit inspection of the trial files and subject eCRFs by such representatives and/or responsible government agencies.

Investigators are required to prepare and submit accurate and timely reports on this study to the governing EC and Biosense Webster.

Table 8: Responsibilities for Preparing and Submitting Reports

Type of Report	Prepared by Investigator For	Time of Notification
Subject withdrawal	Biosense Webster	Should report within 5 working days
Withdrawal of EC approval	Biosense Webster	Should report within 5 working days
Final report	Biosense Webster, EC	Will prepare a final report for the clinical investigation as required per national regulations.
Informed consent not obtained from subject	Biosense Webster, EC	Should report within 5 working days

It is recommended that all eCRF data be entered by the designated site personnel as soon as possible. For AE reporting, refer to the Adverse Event Reporting Requirements and timelines noted within this clinical investigation protocol.

24.1.3 Data Verification and Review

Biosense Webster will track the amount of missing data and contact sites as appropriate to instruct them on steps to minimize missing data and remain compliant with protocol required assessments. Missing or unclear data will be queried as necessary throughout the trial. Biosense Webster will request further documentation such as physician and/or cardiac EP lab procedure notes when complications or device malfunctions/complaints are observed and reported. Biosense Webster will be responsible for auditing the database and confirming the overall integrity of the data.

24.1.4 Final Data Analysis

All exported datasets for analyses will undergo a final data review before final database lock. Once all critical data are monitored and locked, the final analyses of clinical investigation data will be performed.

24.2 Study Record Retention and Archiving

Records and reports for the study will remain on file at the site for a minimum of 10 years or per country specific record retention requirements following notification by the sponsor that all investigations have been terminated or completed. This documentation must be accessible upon request by the CAs, the sponsor, or a designee. The sponsor must approve archiving,

transfer, and destruction of the documentation, in writing, prior to the actual archiving, transfer, and destruction. The investigator must notify the sponsor, in writing, of transfer location, duration, and the procedure for accessing the study documentation.

If the investigator retires, relocates, or withdraws from assuming primary responsibility for keeping the study records, custody transfer per written notice must be submitted to the sponsor indicating the name and address of the person accepting primary responsibility. The EC must be notified in writing of the name and address of the new custodian. Record retention dates must be provided to all parties by the sponsor's corporation.

25. Study Completion, Suspension or Termination

The study end shall be deemed to coincide with the last visit of the last subject. The sponsor will inform the responsible CA within 15 days of the study end in a participating country. In addition, each CA will be notified within 15 days of the global study end.

This study may be temporarily suspended or prematurely terminated at the discretion of the Sponsor. The Sponsor may also terminate a site prior to study completion if the Sponsor believes the site is no longer capable of participating (e.g., cannot fulfill subject enrollment or protocol compliance goals, site suspension by EC). If the study is prematurely terminated or suspended, the PI will promptly inform the EC and will provide the reason(s) for the termination or suspension. The sponsor will inform within 15 days the responsible CA and provide a justification in accordance with MDR Article 77.

If suspension or premature termination occurs, the terminating party shall justify its decision in writing and promptly inform the other parties with whom they are in direct communication. The PI and sponsor shall keep each other informed of any communication received from either the EC or the CA.

If early termination of the study is required due to safety concerns, each site will undergo a monitoring visit to conclude any outstanding issues, collect all outstanding CRF information, verify device accountability, and discuss any other items relevant to the conclusion of the study. Any enrolled subjects will continue to be followed per the study protocol requirements.

If, for any reason, the sponsor suspends or prematurely terminates the study at an individual study site, the sponsor shall inform the responsible CA as appropriate and ensure that the EC is notified, either by the PI or by the sponsor. If the suspension or premature termination was in the interest of safety, the sponsor shall inform all other PIs. The sponsor will inform within 24 hours the responsible CA and provide a justification in accordance with MDR Article 77.

Circumstances that may warrant termination or suspension include, but are not limited to:

- Determination of unexpected, significant, or unacceptable risk to participants
- Demonstration of efficacy that would warrant stopping
- Insufficient compliance to protocol requirements
- Data that are not sufficiently complete and/or evaluable
- Determination of futility

Study may resume once concerns about safety, protocol compliance, data quality is addressed and satisfy the sponsor, EC and regulatory agency.

A clinical study report will be submitted within one year of the study end or within three months of the suspension or premature termination.

26. Data and Publication Policy

Publications and/or presentation of clinical investigation results will be coordinated and governed between Biosense Webster, Inc., the clinical investigation author(s) and if applicable local law. Authorship will be determined prior to development of any manuscript. All information concerning the study, investigational medical device, sponsor operations, patent application, manufacturing processes, and basic scientific data supplied by the sponsor to the investigator and not previously published, are considered confidential and remain the sole property of the sponsor.

As per ISO 141155: 2020 paragraph 5.4. a description of this clinical investigation will be registered in publicly accessible database (<http://www.ClinicalTrials.gov>) and content shall be updated throughout the study. Results will be entered at completion of the clinical investigation.

27. Document Filing

# **Revision History**

| Revision Number | Revision Date
(DD/MM/YYYY) | Reasons for Revision |
|-----------------|-------------------------------|----------------------|
| 1.0             | 08/04/2024                    | Original document    |
|                 |                               |                      |

| Acronym/Abbreviation | Expanded Term                   |
|----------------------|---------------------------------|
| AE                   | Adverse Event                   |
| AT                   | Atrial Tachycardia              |
| CV                   | Cardiovascular                  |
| ICF                  | Informed Consent Form           |
| LA                   | Left Atrium                     |
| LAAO                 | Left Atrial Appendage Occlusion |
| LV                   | Left Ventricle                  |
| NYHA                 | New York Heart Association      |
| PAF                  | Paroxysmal Atrial Fibrillation  |
| PP                   | Per Protocol                    |
| PsAF                 | Persistent Atrial Fibrillation  |
| PVC                  | Premature Ventricular Complex   |
| SAE                  | Serious Adverse Event           |
| SAP                  | Statistical Analysis Plan       |
| TTE                  | Transthoracic Echocardiography  |
| VT                   | Ventricular Tachycardia         |

#### 1 Study Design

This study is a prospective, single arm, non-randomized, open-label, multi-center study. Up to 30 subjects will be enrolled.

Subjects meeting the inclusion / exclusion criteria and who sign the informed consent form (ICF) will be enrolled in this study. The clinical investigation is targeting approximately 4 sites in Europe and Israel.

This study will serve to characterize the performance and safety of using the investigational catheter in procedures for subjects in up to five different subgroups (scar-related AT, PsAF, PAF, VT and PVC). Subjects will be treated per investigator's standard of care and followed until 7 days post-procedure.

The primary objective of this study is to assess the performance and safety of using the investigational catheter.

A secondary objective is to gather physician assessment of deployment, maneuverability, navigational features and imaging quality acquired with the investigational catheter.

#### 2 Treatment Assignment

This is a single arm clinical study and all enrolled patients will use the investigational NUVISION™ NAV Ultrasound Catheter (D-1426-01-SI), which is a sterile, single use, disposable, diagnostic ultrasound imaging catheter designed for intracardiac use. It is built around the core design and technology of the existing NUVISION™ Ultrasound Catheter, 10 Fr (D-1423-01-S).

## **3** Randomization and Blinding Procedures

This is a non-randomized, open-label study.

#### 4 Interval Windows

See Section 14.3 of the study protocol.

#### 5 Levels of Significance

All data will be summarized by descriptive analyses. No formal hypothesis testing will be performed. All confidence intervals will use the two-sided 95% confidence level unless otherwise stated.

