10.3 Subject Disposition

- **Enrolled Subjects:** Patients who sign the ICF.
- **Excluded Subjects:** Subjects who are enrolled but never undergo insertion of the study catheter. Excluded subjects will be subjected to safety event reporting between ICF signature and date of exclusion. Subjects who signed the ICF but are found to be ineligible prior to insertion of the catheter are also considered as excluded.
- **Discontinued Subjects:** Enrolled subjects who have the study catheter inserted but no assessments are performed with it. Discontinued subjects will remain in follow-up for 7 days for safety evaluation.
- **Lost to Follow-up Subjects:** Enrolled subjects of which contact is lost after most recent visit (despite 3 documented attempts to contact the subject).
- **Withdrawn / Early Termination Subjects:** Subjects who withdraw consent for study participation or are withdrawn by the investigator, are terminated from the study prior to completion of all follow-up visits.
- **Completed Subjects:** Enrolled subjects who have not been excluded, discontinued, withdrawn, terminated early, or lost-to-follow-up from the study prior to the final study visit.

11. Responsibilities

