20.4 Analyses to be conducted

20.4.1 General Conventions

Standard descriptive summaries for continuous data include the number of observations with data, mean, standard deviation (SD), median, minimum, and maximum values. These will be referred to as "continuous summaries".

For categorical data, the count and percent will be provided. Percentages will be based on the number of subjects without missing data. For adverse event and device effects data, percentages will be based on the number of subjects in the analysis population being used in the analysis. This will be referred to as "categorical summaries".

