## 6 Analysis Sets

Safety Analysis Set: The Safety Analysis Set will consist of all enrolled subjects who have undergone insertion of the NUVISION™ NAV Ultrasound catheter.

**Per Protocol (PP) Analysis Set**: The PP Analysis Set will include all enrolled subjects who met the study eligibility criteria and in whom assessments were performed with the NUVISION™ NAV Ultrasound catheter.

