## 8 Statistical Analysis Methods

#### 8.1 General Conventions

SAS® version 9.4 or higher will be used for all analysis. Standard descriptive summaries for continuous data include the number of observations with data, number of observations with missing data, mean, standard deviation, median, minimum, and maximum values. For categorical data, the count and percentage will be provided. Percentages will be based on the number of subjects without missing data.

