## 8.5 Analysis of Primary Endpoint(s)

Primary Safety Endpoint is defined as the occurrence of serious adverse events related to the Investigational catheter within 7 days of index procedure. An SAE will be counted as related to the investigational catheter if the relationship to a study catheter is anything other than 'Not Related'.

The number of subjects with SAEs related to the investigational catheter will be summarized in the Safety Analysis Set overall and per procedure type (atrial ablation/ventricular ablation) by System Organ Class and Preferred Term and level of relationship. All tables will present summaries both by subject and by event. If a subject has multiple occurrences of an event within a level of summarization, then for the by-subject summaries only a single occurrence will be counted at each level of summarization at the highest level of severity/relationship; for the by-event summary all events will be counted.

All investigational catheter related SAEs will be listed by System Organ Class and Preferred Term, severity, causality (defined as possible, probable or having a causal relationship to the device and/or procedure), anticipation and outcome.

Primary Performance Endpoint is defined as the completion of imaging required for the study procedure with the NUVISION™ NAV Ultrasound Catheter without resort to non-study ultrasound device(s).

The number of subjects who successfully completed the procedure without resort to a non-study ultrasound device will be summarized overall and per procedure type (atrial ablation/ventricular ablation) for the PP Analysis Set.

A listing of the primary performance endpoint will be provided.

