## 8.9 Subgroup Analysis

Primary and secondary safety endpoints and primary performance endpoint will be further summarized descriptively in the following subgroups:

- 1. Scar-related Atrial Tachycardia
- 2. Persistent Atrial Fibrillation (PsAF)

- Paroxysmal Atrial Fibrillation (PAF)
  Ventricular Tachycardia (VT)
  Premature Ventricular Complex (PVC)

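### Does setting a two-sided 95% confidence level oblige the plan to attach an interval to the primary endpoints?

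*SAP*

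**What the plan says.** SAP section 5 rules out formal testing, makes all summaries descriptive, and adds that "All confidence intervals will use the two-sided 95% confidence level unless otherwise stated". Protocol section 20.1 carries the same sentence. Neither document mentions a confidence interval anywhere else.

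The general convention in SAP section 8.1 is that "For categorical data, the count and percentage will be provided". SAP section 8.5 then handles the two primary endpoints:

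- **Performance:** "The number of subjects who successfully completed the procedure without resort to a non-study ultrasound device will be summarized overall and per procedure type", in the Per Protocol set.
- **Safety:** "The number of subjects with SAEs related to the investigational catheter will be summarized in the Safety Analysis Set overall and per procedure type", with breakdowns by System Organ Class, Preferred Term and level of relationship.

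Protocol section 20.4.6 mirrors this, and both endpoints also get listings. On subgroups, SAP section 8.9 says: "Primary and secondary safety endpoints and primary performance endpoint will be further summarized descriptively in the following subgroups". Again there is no interval. The shells appendix (SAP section 9) contains only template text.

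SAP section 7 sets the sample size at 30 from earlier experience with similar studies, without an assumed rate, a precision target or power.

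**The concern.** A plan that fixes a confidence level normally goes on to say which estimates get an interval and how it is calculated. Here the level is fixed and then never used. Taken literally, the two primary results could be published as a bare 0% and a bare 100%.

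In about 30 subjects such figures look more reassuring than they are. Zero events does not mean a negligible event rate, and results within atrial or ventricular procedures rest on fewer subjects still. Because the sample size has no precision statement behind it, nothing else in the plan tells a reader how much uncertainty to expect. If the method were chosen only after the results were known, the choice could also be questioned. What is at stake is how honestly the precision of the two primary results is conveyed.

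**Working it through.** **Inputs.** Confidence level: two-sided 95%, so 0.025 in each tail and z = 1.96 (SAP section 5, Protocol section 20.1). Number of subjects: at most 30 (SAP sections 1 and 7). Event counts are assumptions, because the documents state no expected rate. The plan has no figure to reproduce: the 30 does not come from a calculation.

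**Step 1. What the missing interval would show at n = 30.** Exact (Clopper-Pearson) limits in the two extreme cases:

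- No events, upper limit = 1 − 0.025^(1/n) = 1 − 0.025^(1/30) = 11.6%.
- All successes, lower limit = 0.025^(1/n) = 0.025^(1/30) = 88.4%.

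A true related-event rate of 5% would give no events in 30 with probability 0.95^30 = 21%. The uncertainty is therefore real.

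**Step 2. Does the unstated method matter?** For the extreme cases the Wilson limits are z²/(n + z²) = 3.84/33.84 = 11.4% and n/(n + z²) = 30/33.84 = 88.6%. With one event or one failure, beta quantiles give the exact limits and the usual score formula gives the Wilson limits:

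| Result | Exact | Wilson |
|---|---|---|
| 0/30 | 0 to 11.6% | 0 to 11.4% |
| 1/30 | 0.1 to 17.2% | 0.6 to 16.7% |
| 29/30 | 82.8 to 99.9% | 83.3 to 99.4% |
| 30/30 | 88.4 to 100% | 88.6 to 100% |

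The two methods differ by about 0.2 percentage points in the extreme cases and by less than 0.6 in the others. No reading of the study would change with the method.

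**Step 3. By procedure type.** The documents give no atrial/ventricular split. If a type had 10, 15 or 20 subjects (assumed), zero events would have an upper limit of 30.8%, 21.8% or 16.8%. These limits show that the cells are small, which the reported denominators show as well.

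**Step 4. Is the denominator open?** No. SAP section 8.5 assigns performance to the Per Protocol set and safety to the Safety set, and SAP section 6 defines both. For adverse events, Protocol section 20.4.1 adds that "percentages will be based on the number of subjects in the analysis population being used in the analysis". SAP section 8.1 does not repeat that line, but section 8.5 names the Safety set, so the two can be read together.

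**Step 5. Does any decision depend on the interval?** There is no hypothesis, no performance goal and no success rule. Protocol section 7.2 gives the purpose as feasibility and safety in support of developing the product. Protocol section 6.3 and SAP section 7 disclaim claims of effectiveness or patient outcome. No error rate, power figure or pass/fail conclusion changes whether an interval is printed or not.

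**The case for a change.** The best case for a change is that it costs almost nothing. An interval is not a test, so it fits a descriptive study, and the sponsor's own text anticipates intervals in the same paragraph that excludes testing. Naming the method in advance would remove any later choice, and a first-in-human report that shows 0% with an upper limit is better than one that shows 0% alone.

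Most of this is fair as reporting advice. It does not show a fault in the plan. The sentence governs intervals if they are made, so leaving it unused contradicts nothing, and the plan does not forbid adding them to the report. The worry about a later choice of method carries little weight when the methods agree as closely as in Step 2. The cost is also a little higher than it looks: Protocol section 20 presents itself as the study's statistical analysis plan and mirrors the SAP, so an edit to the SAP alone would put the two documents out of step.

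A further argument concerns performance. Protocol section 10.3 defines Discontinued subjects as "Enrolled subjects who have the study catheter inserted but no assessments are performed with it", whereas the Per Protocol set in SAP section 6 takes only those "who met the study eligibility criteria and in whom assessments were performed with the" catheter. Possible failures could therefore fall outside the performance result. That question is legitimate, but it concerns the analysis set. It exists with or without an interval, and an interval on the Per Protocol set would not answer it.

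**Conclusion.** No change follows. The observation is accurate: a level is set, and no endpoint is given an interval or a method. It is a gap in detail, and no figure or rule in the plan is wrong because of it. Followed as written, the plan produces correct counts, percentages on named analysis sets, and listings. Anyone can obtain the limits from these, at best 11.6% (upper, 0/30) and 88.4% (lower, 30/30) if all 30 subjects are analysed, and wider with fewer.

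This conclusion rests on the study staying descriptive, without a performance goal or an effectiveness claim. It also rests on each percentage being reported with its count and denominator. Deleting the unused sentence would tidy the text but would alter nothing that the trial does or reports.
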